8.2 Populations

The data analysis will be performed in:

• Efficacy Population (EP): The primary efficacy population will consist of patients who have a confirmed GIST, were eligible for the study and signed an informed consent, and were included in the study.

The EP will be the primary analysis population. For the potential purposes of reporting the data to the regulatory authorities the EP population will be used.

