	 deficiency. 4. Presence of neurofibromatosis-1. 5. R2 resection of the primary tumour or metastasis. 6. Patient with inability to grant reliable informed consent. 7. Inability to comply with the scheduled follow-up. 8. Progressive disease during imatinib or other systemic treatments for GIST before or after surgery/REA of the
STUDY TOEATMENT	metastases. Study group: Discontinuation of imatinib
STUDI IREATMENT	No imatinib or other anti-cancer treatment will be administered.
ASSESSMENTS:	 Primary: Progression-free survival (PFS) is defined by the time interval between the date of imatinib discontinuation and the date of first detection of GIST progression or death, whichever occurs first. Patients alive without progression are censored on the date of last follow-up Secondary:
	 Overall survival (the time period between the date of imatinib discontinuation and the date of death). Quality of Life (EQ-5D instrument).
	 Exploratory: To explore the relationship between study endpoints and blood biomarkers including, but not limited to, KIT/PDGFRA mutations in cell-free circulating DNA in plasma and circulating growth factor and cytokine levels. To explore the relationships between study endpoints and biomarkers in resected tumors prior to study entry. Changes in the blood cell counts and blood biochemistry after stopping imatinib as compared to the values on

	imatinib (includes comparisons in blood cell counts, serum transaminases, creatinine, and electrolytes between the baseline values measured on imatinib and the values measured at 2, 5 and 8 months after stopping imatinib).		
Pre-planned interim analysis:			
	• 1-year PFS in the first 15 patients included. The study is		
	terminated if 10 or more of the 15 patients (≥ 67 %) have		
	progression of disease or withdraws from the study within		
	the first 12 months from the date of study entry.		
STATISTICAL	This is a superiority study as compared with historical controls		
CONSIDERATIONS	regarding the main endpoint (PFS). Based on historical data,		
	discontinuation of imatinib in patients with metastatic GIST is		
	associated with rapid recurrence/progression. In the BRF-14		
	study where patients were randomised to discontinue imatinib at		
	1 and 3 years on treatment, the 2-years PFS was 10 % and 16 %,		
	respectively. Based on these observations, the historical 3-year		
	PFS can be assumed to be 15 %. An improvement in 3-year PFS		

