3.2.2 Inclusion and exclusion criteria

Inclusion criteria:

To be eligible for inclusion in the study, each patient must fulfil each of the criteria below.

1. Age \geq 18.

2. Morphological and immunohistochemical documentation of GIST (immunostaining for KIT/(CD117) and/or DOG-1 (anoctamin-1)) must be positive on a tumour sample. Patients with demonstrated mutation in *KIT* or *PDGFRA* may be entered to the study despite negative immunostaining for KIT and DOG-1 provided that tumour histology is compatible with GIST.

3. > 5.0 years of treatment with imatinib for metastatic disease when the breaks in imatinib administration are taken into account.

4. No more than 3 detectable metastases in the liver and/or in the abdomen in imaging of the abdomen and the pelvis during the course of the disease or at surgery.

5. Confirmed metastatic GIST in history by radiology, histology, or both.

6. Macroscopically complete resection of all metastases (either R0 or R1 surgery). Patients who have microscopically infiltrated margins (or suspected microscopical infiltration, R1) are

allowed to enter the study. RFA of liver metastasis is allowed in place of surgery. Patients whose oligometastatic disease had disappeared completely so that no remaining target lesion for surgery or RFA can be identified (including absence of residual cyst-like lesions) are allowed to enter the study.

7. Eastern Co-operative Oncology Group (ECOG) performance status ≤ 2 .

8. Patient has provided a written, voluntary informed consent prior to study entry and any study-specific procedures.

Exclusion criteria:

To be eligible for inclusion in the study, each patient must not have any of the criteria below.

1. Patients with metastases outside of the abdomen (e.g. in the bones or lungs).

2. Not willing to donate tumor tissue and/or blood samples for the molecular studies that aim at predicting of GIST recurrence.

- 3. Presence of an *SDH* mutation or other evidence for SDH deficiency.
- 4. Presence of neurofibromatosis-1.
- 5. R2 resection of the primary tumor or metastasis.
- 6. Patient with inability to grant reliable informed consent.
- 7. Inability to comply with the scheduled follow-up.

8. Progressive disease during imatinib or other systemic treatments for GIST, or before or after surgery/RFA of the metastases.

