3.5.3 Tumour assessments

Tumour assessments should be performed with the same method (CT or MRI) throughout the study. All assessments should be performed within 28 days of the scheduled day of assessment, and whenever clinically indicated otherwise.

Radiological tumour assessment at inclusion and if progression should be stored at the local study site and submitted for central review per request.

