8.1 Sample size and power considerations

The sample size calculation is based on the analysis of the primary objective: PFS at three years after discontinuation of imatinib. PFS is defined as the time interval between the date of discontinuation of imatinib and the date of first detection of GIST progression or death, whichever occurs first. The progression date is defined as the date when the physician first suspects GIST progression in a sequence of events that leads to the diagnosis of progressive GIST. This date will be documented on the CRF by the investigator and will be used as such in the analysis.

The power of the study was derived from comparison to historical controls regarding the main endpoint (PFS). Based on historical data, discontinuation of imatinib in patients with metastatic GIST is associated with rapid recurrence/progression. In the BRF-14 study where patients were randomized to discontinue imatinib at 1 and 3 years of treatment, the 2-years PFS was 10 % and 16 %, respectively. The historical 3-years PFS is expected to be 15 %. An improvement in 3-years PFS from 15 % to 35 % in the study arm is considered clinically significant. To find this effect with 80% power using a one-sided significance level of 0.05, 26 patients are needed. To allow a drop-out rate of 15 %, 31 patients will be included in the trial (power 0.8, one-sided alpha 0.05).

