11.1 Administrative procedures

11.1.1 Changes to the protocol

Changes (excluding minor administrative, technical or grammar changes) to this protocol requires a written protocol amendment that must be approved by the Principal Investigator Ethics Committee, and competent authorities (medical agency) where relevant, before implementation.

Amendments significantly affecting the safety of the patients, the scope of the investigation or the scientific quality of the study require additional approval by the Institutional Review Board/Independent Ethics Committee/Research Ethics Board (IRB/IEC/REB) and by the regulatory authorities. Examples of amendments requiring such approval are:

- 1. significant changes in the study design,
- 2. increases in the number of invasive procedures to which subjects are exposed,
- 3. addition or deletion of a test procedure required for safety monitoring.

These requirements for approval should in no way prevent any immediate action from being taken by the investigator in the interests of preserving the safety of all patients included in the trial. Examples of administrative changes not requiring formal protocol amendments and IRB/IEC/REB approval include:

- 1. changes in the staff,
- 2. minor changes to the exclusion or inclusion criteria used to select study patients,

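### Section 8.2 makes eligibility a condition for the only analysis population without tying it to the registration decision, so patients who stopped imatinib could be excluded after their outcome is known

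*Protocol*

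**What the plan says.** Section 8.2 defines one analysis set, which it calls the Efficacy Population (EP). Its definition reads: "The primary efficacy population will consist of patients who have a confirmed GIST, were eligible for the study and signed an informed consent". The same sentence adds inclusion in the study as a further condition. The EP is named as the primary population and as the one for any reporting to authorities. No set of all registered patients, or of all patients who stopped imatinib, is defined.

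Section 3.3 says that patients who satisfy the criteria are registered, and section 3.4.1 has them stop imatinib within 14 days of registration. Section 8.2 does not refer back to that decision.

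Two provisions let eligibility be looked at again after entry:
- The monitoring plan (Appendix I) requires the eligibility criteria to be verified in 100% of patients. A site is visited early after its first patient enters, and then once every 12 months while it has patients on study.
- Section 3.5.3 states: "Radiological tumour assessment at inclusion and if progression should be stored at the local study site and submitted for central review per request". Section 6 repeats this.

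The interim rule in section 8.4 counts the first 15 patients included and states no eligibility condition.

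**The concern.** Being eligible and being included are separate conditions in section 8.2. A patient who was registered, stopped imatinib and was later judged ineligible therefore does not belong to the EP as it is worded. Nothing in the definition limits that judgement to what was known at registration.

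The later checks can fall after progression. Imaging is scheduled at months 2, 5, 8 and 11, while routine monitoring visits may be a year apart. Section 1.5 reports that almost all patients who stopped in the earlier discontinuation trial progressed within 2 years. Only a patient who has progressed has a progression scan, so a request to re-read the pair of scans would concern a progressor. If the inclusion scan were then read as showing a lesion, the requirement of no detectable disease would be in doubt.

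The trial has one arm and is judged against a fixed historical 15%, so no control group exists in which late exclusions could balance. A patient removed in this way did stop imatinib, and recurrence after stopping is what the trial sets out to measure. The interim and final analyses could also rest on different sets of patients.

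**Working it through.** **Inputs (section 8.1).** The benchmark is 15% and the target 35%: "An improvement in 3-years PFS from 15 % to 35 % in the study arm is considered clinically significant". On size: "To find this effect with 80% power using a one-sided significance level of 0.05, 26 patients are needed". With 15% drop-out the total is 31. The number of patients removed, k, is not in the documents. It is an assumption here, shown from 0 to 5, where 5 = 31 − 26.

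**Step 1: the plan's own sample size.** One-sample normal approximation, one-sided 0.05, power 80%:

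n = [(1.645·√(0.15·0.85) + 0.842·√(0.35·0.65)) / 0.20]² = 24.4, so 25.

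The arcsine version gives 27.9, so 28. The stated 26 lies between the two. Drop-out: 26 / 0.85 = 30.6, so 31. The sample size is not in question.

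**Step 2: shift in the estimate.** Suppose only progressors are removed and there is no other censoring. The expected 3-year PFS is then 31·p / (31 − k), where 31·0.35 = 10.85 and 31·0.15 = 4.65.

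**Step 3: illustrative test.** The protocol states no success count; section 8.3 specifies Kaplan-Meier estimation. To show the effect on a decision, take the smallest r with P(X ≥ r | n, 0.15) ≤ 0.05, where n = 31 − k are analysed. The type I error over everyone who stopped is then P(X ≥ r | 31, 0.15), because the count of successes still comes from all 31.

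| k removed | n analysed | Estimate, true 35% | Estimate, true 15% | Required count r | Type I error over all 31 |
|---|---|---|---|---|---|
| 0 | 31 | 35.0% | 15.0% | 9 | 0.034 |
| 1 | 30 | 36.2% | 15.5% | 9 | 0.034 |
| 2 | 29 | 37.4% | 16.0% | 9 | 0.034 |
| 3 | 28 | 38.8% | 16.6% | 8 | 0.082 |
| 4 | 27 | 40.2% | 17.2% | 8 | 0.082 |
| 5 | 26 | 41.7% | 17.9% | 8 | 0.082 |

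Example: 8 of 31 (25.8%) gives p = 0.082 and fails. With three progressors removed, 8 of 28 (28.6%) gives p = 0.049 and just passes.

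**Step 4: the other direction.** Removing one ineligible non-progressor lowers the expected estimate at a true 35% to (10.85 − 1) / 30 = 32.8%. A result of 9 of 31 (p = 0.034) would become 8 of 30 (p = 0.070) and no longer pass. The direction of any bias therefore depends on who is removed.

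**The case against.** The strongest reply is that section 3.3 allows only patients who satisfy the criteria to be registered, so the natural reading of eligibility in section 8.2 is status at entry, and few patients would be affected. No section says that central review can reverse eligibility or take a patient out of the analysis. The one systematic check, source verification, covers every patient whatever the outcome. Criteria such as length of imatinib treatment, NF-1 or SDH deficiency could disqualify non-progressors as readily as progressors. Who judges eligibility, and when, is also commonly left to a statistical analysis plan, which is not shown.

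Much of this stands. The protocol permits late exclusion but does not order it, and the frequency is unknown and may be low. The absence of a named assessor or cut-off date is not itself a finding. What remains is that the protocol fixes the population, lists eligibility apart from inclusion, and leaves the natural reading unstated.

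A reader might infer three stronger things that the documents do not support:
- That removal works only in favour of the trial. Step 4 shows that it need not.
- That the criteria themselves can be moved to remove patients, because section 11.1.1 lists "minor changes to the exclusion or inclusion criteria used to select study patients" among changes needing no formal amendment. That item is limited to minor changes and concerns the selection of patients. Nothing in it removes a patient already included.
- That the two wordings of exclusion 8, in the synopsis and in section 3.2.2, show outcome-related removal. They are a drafting conflict to be reconciled as a separate matter.

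**Conclusion.** The concern holds as a weakness in a stated rule. The only defined population allows exclusions after the outcome is known, in a design where the set of patients counted largely decides the result. Upward bias is plausible, because re-reading of paired scans would concern progressors, but it is not established.

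The size depends on an assumed number of removals. One or two progressors removed shift the estimate by about 1 to 2 percentage points at a true 35% and leave the required count unchanged. Three is the smallest number that lowers it. The 8.2% is a worst case: it requires three to five progressors, and no non-progressors, to be removed in every hypothetical repetition of the trial. It also rests on an exact binomial rule that the protocol does not state and on known 3-year status for all 31.

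**What to change.** In section 8.2, define the primary population as all registered patients who discontinued imatinib, whatever is found about eligibility afterwards. Keep the present EP as a sensitivity analysis, with eligibility judged only on information available at registration. This also brings the final analysis into line with the interim rule, which counts patients as included.

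The cost is a change of wording. A few ineligible patients may stay in the primary analysis, and the estimate may be slightly lower. The sample size stays at 31. With all 31 analysed and their 3-year status known, the illustrative exact test has type I error 0.034 and power 0.811.

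Separately, reconcile the two versions of exclusion 8 in the synopsis and section 3.2.2.

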8.3 Efficacy evaluation

Final analysis

The study is designed to investigate the proportion of patients who are alive without GIST progression after a median follow-up of approximately 36 months after study entry.

The primary endpoint PFS will be measured from the date of discontinuation of imatinib to the date of first documentation of progression or death (from any cause), whichever occurs first. Patients alive without GIST progression are censored on the date of last follow-up. Survival estimates will be calculated using the Kaplan-Meier estimator. Comparison between subgroups, if relevant, will be based on the log-rank test and univariate Cox models. Estimates for hazard ratios will be provided with 95% confidence intervals.

The overall subgroup effects will be quantified by a hazard ratio, which will be estimated using a Cox proportional hazards regression model (or a suitable generalisation such as concordance regression, ⁴³ if the model assumptions for the Cox model are not met) with the discontinuation group in the model.

A number of exploratory analyses may be performed for the primary endpoint:

• Log-rank test and Cox proportional hazards model (or a suitable generalisation) stratified by relevant parameters such as, but not limited to the tumour site (gastric or non-gastric),

localization of metastasis (liver, intraperitoneal, both), metachronous and synchronous metastasis.

• A Cox proportional hazard model (or a suitable generalisation) estimating survival while adjusting for the established prognostic variables. In addition, the centre or country and other relevant baseline variables may be included in the model.

Overall survival will be analysed as a secondary endpoint in the final analysis, based on the early data detected by the time of the analysis. Overall survival will be measured from the date of discontinuation of imatinib to the date of death resulting from any cause. Patients alive are censored at the time of last follow-up. Similar methods as for the primary variable will be used in the data analysis.

Exploratory analyses will be carried out to evaluate the data of the molecular analyses carried out. The statistical analyses will be dependent on the biological factors investigated and the analysis methodology used, and will be defined separately for each molecular study.

8.4 Number of analyses

Two analyses are planned, one interim and one final analysis. The interim analysis is planned in the first 15 patients included. The analysis will be performed when 15 patients will have one year of follow-up and the following key parameters will be checked: the enrolment of the patients and the rate of progression. The study is terminated if 10 or more of the 15 patients (\geq 67 %) have progression of disease or withdraws from the study within the first 12 months from the date of study entry. The final analysis will be performed when the patients without an event have a median follow-up time \geq 36 months.

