3.1 Overall study design

This is an open-label, one-group, multicentre, phase II study conducted to investigate PFS in patients treated with imatinib longer than 5 years for oligo-metastatic GIST (\leq 3 metastases) and who have no detectable overt GIST lesions in CT/MRI imaging following complete surgical resection (R0/R1-resection), RFA of the metastases, or after systemic treatment for oligometastatic GIST.

The study participants are assigned to stop imatinib and will be monitored for cancer progression longitudinally with physical examination, measuring blood cell counts and blood chemistry, and with CT/MRI examinations. A pre-planned interim analysis will be carried out when the first 15 patients in the study have been follow-up of for one year. The study will be terminated if 10 or more of the 15 patients (\geq 67 %) have recurrence of GIST or discontinue the study within the first 12 months from the date of study entry. The primary analysis of the study will be carried out when the median follow-up time of the study patients is at least 36 months. A total of 31 patients will be enrolled. If GIST recurs, imatinib will be restarted at the same dose as at study entry.

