3.4.2 Patient discontinuation in the study

The reasons for patient discontinuation in the study must be captured on the CRFs. If the patient discontinues the study, the reason is categorized in the CRFs as one of the following:

- 1. Withdrawal from the study
- 2. GIST progression
- 3. Death (from GIST or from an inter-current cause)
- 4. Other (for example, severe protocol violation, administrative problems)

Relevant information that is related to the reason for study discontinuation, including possible contributory factors, will be included on the CRF.

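### The interim termination rule counts different patients as failures in section 3.1 than in section 8.4 and the synopsis, and does not say that the tenth failure already settles it

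*Protocol*

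**What the plan says.** Three places state the termination rule, all with the threshold of 10 of 15.

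- **Section 8.4 and the synopsis** count patients who "have progression of disease or withdraws from the study within the first 12 months from the date of study entry".
- **Section 3.1** counts patients who "have recurrence of GIST or discontinue the study within the first 12 months from the date of study entry".

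Section 3.4.2 lists the reasons for discontinuing the study as separate CRF categories. Besides GIST progression they are "1. Withdrawal from the study", "3. Death (from GIST or from an inter-current cause" and "4. Other (for example, severe protocol violation, administrative problems". Withdrawal is thus one kind of discontinuation, distinct from death and 'other'.

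The synopsis labels the interim quantity as 1-year PFS in the first 15 patients. PFS, as defined in the synopsis and in sections 8.1 and 8.3, includes death.

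On timing, section 8.4 says: "The analysis will be performed when 15 patients will have one year of follow-up". Section 3.1 agrees. The 12-month window runs from study entry, whereas PFS runs from imatinib discontinuation. Section 3.4.1 puts discontinuation within 14 days of inclusion.

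**The concern.** A termination rule should give one answer on one dataset. Here a death without progression, or an exit classed as 'other', counts under section 3.1 but not under section 8.4 or the synopsis rule. The synopsis is also at odds with itself: its label includes death and the rule beneath it does not. If the interim count comes out near the threshold, whoever applies the rule would have to choose between definitions with the results in view.

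There is a second, smaller gap. The rule is a fixed count, and failures can only accumulate. Once ten of the first 15 patients have failed within their 12 months, the outcome is settled. The only stated assessment comes later, when all 15 have a year of follow-up, and nothing is said about enrolment meanwhile. Section 3.5.8 accepts that stopping imatinib may raise the risk of progression, so entries made after the criterion is already met matter.

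**Working it through.** **1. The protocol's own figure.** 10/15 = 66.7%, which matches the stated 67%. The protocol gives no probability of stopping.

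**2. The rules side by side**

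| Exit within 12 months | 3.1 | 8.4 and synopsis rule | PFS event |
|---|---|---|---|
| Progression/recurrence | counts | counts | yes |
| Withdrawal | counts | counts | no |
| Death without progression | counts | does not count | yes |
| Other | counts | does not count | no |

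Example: 9 progressions or withdrawals plus 1 death without progression gives 10/15 under 3.1 (terminate) and 9/15 under 8.4 (continue).

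**3. How often the readings disagree.** Let q be the 12-month probability of progression or withdrawal, and d that of death or 'other' as the first exit. The 3.1 count is never below the 8.4 count, so

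P(disagree) = P(Bin(15, q+d) ≥ 10) − P(Bin(15, q) ≥ 10).

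The protocol gives neither q nor d, so both are assumed.

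| q | P(stop), 8.4 | disagree, d = 1% | d = 2% | d = 5% |
|---|---|---|---|---|
| 0.30 | 0.004 | 0.1% | 0.2% | 0.9% |
| 0.50 | 0.151 | 1.9% | 4.0% | 11.0% |
| 0.60 | 0.403 | 3.1% | 6.3% | 16.1% |

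For example, at q = 0.50 and d = 0.05: 0.261 − 0.151 = 0.110. At q = 0.60: 0.564 − 0.403 = 0.161.

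**4. Plausible 12-month failure rates.** Constant hazard is assumed, applied to the PFS figures in section 8.1.

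- Three-year PFS 35%: 1 − 0.35^(1/3) = 0.295, P(stop) = 0.003.
- Three-year PFS 15%: 1 − 0.15^(1/3) = 0.469, P(stop) = 0.10.
- Two-year PFS 16%: 1 − √0.16 = 0.600, P(stop) = 0.40.
- Two-year PFS 10%: 1 − √0.10 = 0.684, P(stop) = 0.67.

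**5. When the outcome is settled.** Simulation with random accrual at a constant rate, capped at 31 patients, and hazard −ln(1−q)/12 per month; 40,000 runs per scenario. The look is 12 months after the 15th entry. The table gives means over trials in which the rule is met, with q here standing for all failures that count.

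| Patients/year (assumed) | Months from tenth failure to look, q = 0.469 / 0.600 / 0.684 | Further entries in that time |
|---|---|---|
| 3 | 10.1 / 12.0 / 14.2 | 2.5 / 3.0 / 3.5 |
| 6 | 7.6 / 8.9 / 10.2 | 3.8 / 4.5 / 5.1 |
| 10 | 6.2 / 7.3 / 8.3 | 5.1 / 6.0 / 6.9 |
| 15 | 5.3 / 6.3 / 7.1 | 5.6 / 6.8 / 7.9 |

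These runs treat progression as known when it occurs. Detection only at scheduled scans would shorten the interval somewhat.

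**The case against.** **The difference may rarely matter.** Deaths without progression within a year may be few in patients with ECOG status of 2 or better. The 1-year PFS label in the synopsis also suggests that death was meant to count. Both points have weight, and the first is why the disagreement is only a few percent at low d. But the label does not change the rule sentence in the synopsis or in 8.4, and it says nothing about 'other' exits.

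**A fixed-time look is conventional.** This is true, and nothing in the protocol forbids ending the study sooner. The timing point is a missing trigger, not a prohibition. Its size depends on accrual and hazards that the protocol does not state, and the hazards come from a population that section 1.5 calls less selected than this one.

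A reader might infer more than the document supports:

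- *That the rule is the only protection for patients.* It is not. Patients have scheduled imaging (Table 1, section 3.5.1), recurrence ends the imatinib-free period (sections 3.1 and 3.4.1), and section 11.1.1 preserves immediate action for safety. It is the only study-level stopping rule stated.
- *That the readings conflict in 15-21% of trials.* That is P(exactly 9 of 15) at failure rates of 50-60% (0.153 and 0.207). A reversal from 9 also needs a death or 'other' exit among the remaining six patients.
- *That counting withdrawals as failures at the interim contradicts section 8.3*, where "Patients alive without GIST progression are censored on the date of last follow-up". A stopping rule and a Kaplan-Meier estimate serve different purposes and may treat withdrawals differently.
- *That the start dates differ materially.* The gap is at most 14 days and could matter only for an event close to month 12.

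**Conclusion.** The contradiction stands as written: two definitions of failure govern one termination rule, and the same data can give opposite decisions. Its expected size is modest: about 2-6% of trials for an assumed death/other rate of 1-2% and 11-16% for 5%, when progression/withdrawal is 50-60%, and below 1% when it is 30%. All these rates are assumptions.

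Recognising the criterion at the tenth failure is a worthwhile addition, not the correction of an error. It would come about 5-14 months before the scheduled look and avoid about 3-8 entries. This assumes accrual of 3-15 patients/year and 12-month failure of 47-68%, and applies only when the rule is met (about 10% to two thirds of trials over that range).

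The sample size is unaffected. Earlier recognition leaves the probability of stopping as it is, but settling which exits count does not: at q = 0.50, adding 5 points moves it from 0.151 to 0.261.

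**What to change.** 1. Reconcile the synopsis, section 3.1 and section 8.4 into one failure definition in identical words. It should state whether death without progression counts and whether 'other' discontinuation counts. If the 1-year PFS label stays, the definition must agree with it on death.
2. Use one start date for the 12-month window in all three places. This is minor.
3. State the probability of stopping under the agreed definition for a range of 12-month failure rates, since it depends on what is counted.
4. State that the 10-of-15 criterion is recognised as soon as the tenth failure occurs among the first 15 patients, and otherwise is assessed when all 15 have 12 months of follow-up.

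The cost is a wording amendment and a running count of events at the study secretariat. The 10-of-15 threshold can stay.
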